### **Continuous glucose monitoring (CGM)**

The sensors (Abbott Diabetes Care Inc., Alameda, CA, USA) will be fixed to the anterior portion of the upper arm with a small adhesive patch. These sensors will be worn for 14 days to determine free-living glycaemic control.

### **Habitual Physical Activity and Sleep (accelerometry)**

Physical activity (PA) and sleep will be assessed using wrist-worn accelerometers (GENEActiv, Activinsights, Kimbolton, Cambridge, UK). These devices have previously been validated for use in healthy adult populations (7) and are extensively used in clinical studies. The GENEActiv accelerometers will measure triaxial movement acceleration in gravity (g) units ( $1\text{ g} = 9.81\text{ m/s}^2$ ) at a frequency of 100Hz continuously over a period of 7 days. The Euclidean norm (magnitude) of signals from the three axes minus 1 g (with negative numbers rounded zero) will be used to quantify acceleration due to movement in mg ( $1\text{ mg} = 0.00981\text{ m/s}^2$ ) (33). Following the measurement periods, data will be downloaded using manufacturers software and processed in R (R Core Team, Vienna, Austria) using the open source GGIR software package (<http://cran.r-project.org>) following completion of the study. Previously validated acceleration threshold values (in healthy adults) will be used to quantify the time (minutes/day) spent on average in each intensity category: total PA, and separately for light, moderate, vigorous intensities and the composite category moderate-vigorous PA (MVPA). To facilitate comparison with current national PA guidelines PA, average MVPA accumulated in bouts of at least 10 minutes will also be calculated.

Sleep variables will be determined from accelerometer data using an open source sleep detection algorithm in GGIR software. Sleep metrics derived using this method have demonstrated good levels of agreement with both self-report measures of sleep and polysomnography (the gold standard). The method of accelerometer based sleep quantification used in this study is described in detail elsewhere (34). Briefly, wrist-worn triaxial accelerometers allow approximation of the angle of orientation of the arm relative to the horizontal plane. Periods of sleep are defined as nocturnal periods characterised by minimal movement frequency and magnitude of changes to the angle of the arm which does not include day time sleep. Time in bed will be defined as the onset of the first period of sustained inactivity (as measured by changes of less than 5 degrees in a rolling 5 minute window) to the end of the last period of inactivity. Sleep duration is the sum of all recorded periods of sleep. Sleep efficiency can then be calculated as the sleep duration as a proportion of time in bed.

Periods of accelerometer non-wearing will be identified using the range and standard deviation (SD) of acceleration values at each axis, calculated for rolling 60 minute windows. Non-wearing will be indicated if the SD is  $<13.0\text{ mg}$  or if the range of values is  $<50\text{ mg}$  for two of the three axes. A full explanation of this method can be found elsewhere (33). To allow effective assessment of habitual PA and sleep, measurement days when the accelerometer is worn for less than 16 hours will be excluded from the final analyses (33). Participants who recorded less than 4 days of 16 hours will also be excluded.

### **Oxygen saturation**

An SpO2 monitor (Equivital EQ02, Hidalgo, UK) will be set up at the participant's home. Participants will wear the monitor at all times during exposure to hypoxia. If saturation falls below (65%) an alarm will be sounded. This system also records beat to beat heart rate and will store the data on the device until it is collected. Participants will also be asked to maintain a diary of the time spent in the tent.

### **Diet diary**

Participants will be asked to record a dietary diary and photograph meals for all 10 days of the intervention in order to try and replicate it in both conditions. This is an important step to enable us to assess any changes in the gut microbiome. We appreciate that this is a significant participant burden and it will be discussed in the section below.

### **Biochemistry**

Fasting venous blood [glucose] peak venous blood [glucose] during OGTT, Homeostatic Model Assessment for Insulin Resistance (HOMA-IR), hormonal markers of appetite (e.g. incretins, leptin and ghrelin\*), food intake, markers of inflammatory status (e.g. interleukin-6; nitrite), redox balance (TNFa; SOD), HIF-1 $\alpha$  and extracellular HSP70. We will also include an untargeted metabolomics strategy using two ultra performance liquid chromatography-mass spectrometry assays to measure the relative concentration of up to 2000 metabolites (plasma and urine). \* For analysis of gut hormones, sample collection tubes need to be treated in specific ways. For incretin analysis (i.e. GLP-1 and PYY) we will prime the EDTA tubes with a 10  $\mu$ l of DDP-IV inhibitor per mL of whole blood and 100  $\mu$ l of aprotinin. The tubes are chilled on ice, and remain on ice until centrifuged. For analysis of leptin and Desacyl-Ghrelin 100  $\mu$ l of aprotinin is added to an EDTA tube and for Acyl-Ghrelin and additional 20  $\mu$ l of Pefabloc is added. Following centrifugation, both Ghrelin samples will be treated again (475 $\mu$ l of plasma to 25 $\mu$ l of Pefabloc).

### **Gut microbiota**

Stool samples will be frozen at -80°C within 12 hours of collection. Bacterial DNA will be extracted using the QIAamp PowerFecal Pro DNA kit according to the manufacturer's instructions (51804, Qiagen, USA) at the end of data collection. The purified extracted DNA will be frozen at -80°C. The extracted DNA will be delivered to the University of Southampton, National Oceanography Centre, for PCR amplification of the 300 bp reads, V3-4 region of the 16S rRNA gene. DNA samples will be depleted for host DNA and enriched for bacterial DNA using primers spanning the full-length prokaryote-specific 16S rRNA amplicon. In this way, host DNA from the individuals will not be analysed, preventing any issues with personal identification. 16S rRNA sequencing libraries will be generated for the Illumina MiSeq sequencer. Sequenced 16S rDNA sequences will be compared against the SILVA database of known 16S rDNA sequences for taxonomic classification.

Comparisons of the gut microbiome will be made using the Alpha ( $\alpha$ ) diversity levels on basis of the observed diversity, Chao1 diversity and Shannon diversity metrics. Variability between the cohorts will be identified based on principal coordinates analysis. Significantly differentially abundant taxa will be identified between each cohorts' sample based on the use of generalised linear models using the DESeq2 package in R, using a fold change threshold of

2-fold difference between the cohorts with a p value (adjusted for multiple testing using Benjamini and Hochberg correction) <0.05.

Faecal samples will also be analysed (in collaboration with UCL) for short-chain fatty acids (acetate, propionate, butyrate, isobutyrate, valerate, isovalerate, hexanoate), alcohols (ethanol, 1-propanol, 2-propanol, butanol, isobutanol, pentanol) and indoles (bacterial metabolites of tryptophan that have immunomodulatory effects).

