#### 4. BACKGROUND AND RATIONALE

Type 2 diabetes mellitus (T2DM) is a metabolic condition characterized by progressive insulin resistance and chronic hyperglycemia (high blood glucose concentrations) (10). Hyperglycaemia increases the risk of both micro- and macrovascular damage, whilst interventions that reduce blood glucose mitigate this risk (32). Weight loss, achieved through exercise and dietary modification, is effective at reducing hyperglycaemia (22). However, despite the clear benefits of exercise and weight loss, diverse psychological, sociological and logistical factors can make it difficult for some individuals with T2DM to initiate, or adhere to, these lifestyle interventions (1, 9). With the number of people with T2DM continuing to rise, this pandemic is expected to reach 700 million people by 2045 (24). Thus, there is a clear need for cost-effective interventions that can effectively improve glycaemic control in people with T2DM and which people will adhere to.

A simple exposure to a lowered concentration of inspired oxygen (i.e. hypoxia) may represent such an intervention. In addition to the beneficial effects on glucose homeostasis that have been reported following a single acute hypoxic exposure, repeated intermittent, or continuous, hypoxic exposure may also have therapeutic potential in individuals with T2DM. In rodent models, daily hypoxic exposures returned fasting blood [glucose] to normal levels and increased glucose transporter 4 translocation in mice with T2DM (6, 35). Similar effects on glucose homeostasis have been shown in overweight humans (17) and those with insulin resistance, (during intermittent hypoxic training) which was explained, at least in part, by reduction in body mass (~ 1.2 kg) (27).

Another mechanism for hypoxia induced weight loss could be a shift in the gut microbiome. The gut is a hypoxic environment and as the body becomes systemically hypoxic, anaerobes are likely to become more dominant (11). Some anaerobes are fermenters which not only produce alcohol but also short and medium chain fatty acids which can be metabolised (2, 25). Specifically, the hypoxia-inducible factor (HIF) pathway is attenuated with upregulation of the pyruvate kinase 1 and subsequent inhibition of pyruvate dehydrogenase (21). Moreover, the gene encoding PPAR is selected for during high altitude which leads to a shift in fatty acid

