### Hypothesis

We hypothesise that 10-days of overnight moderate hypoxia will:

1. Improve glucose control
2. Improve insulin sensitivity
3. Reduce appetite / food intake
4. Reduce body mass
5. Improve inflammatory status
6. Improve redox balance
7. Increase gut anaerobe content
  
8. Maintain habitual physical activity
9. Have no effect on sleep quality

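### Hypothesis 7 (more gut anaerobes) has no matching pre-specified measure or test

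*Combined protocol and SAP*

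**What the plan says.** The Synopsis and the Hypothesis list in section 6 both predict that hypoxia will "Increase gut anaerobe content". Section 4 gives the reasoning: the gut is already hypoxic, and with systemic hypoxia "anaerobes are likely to become more dominant".

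The secondary outcomes in 6.2 and 7.2 say only that the gut microbiome will be assessed. The analysis is in 10.4 (Gut microbiota), which begins "Comparisons of the gut microbiome will be made using the Alpha" diversity and has four parts:

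- within-sample measures: "observed diversity, Chao1 diversity and Shannon diversity metrics";
- ordination: "Variability between the cohorts will be identified based on principal coordinates analysis";
- a taxon screen: "Significantly differentially abundant taxa will be identified between each cohorts' sample", using DESeq2 and requiring a "2-fold difference between the cohorts with a p value (adjusted for multiple testing using Benjamini and Hochberg correction) <0.05";
- faecal short-chain fatty acids, alcohols and indoles.

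Reads are classified against the SILVA reference. Section 14.2 names no microbiome variable, and 14.4 says that no analysis plan is needed beyond what the protocol contains. Stool is collected at visits 2 to 5, of which 2 and 4 are pre-exposure and 3 and 5 post-exposure.

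**The concern.** The hypothesis concerns one quantity, the amount of anaerobes, and one direction. No section defines that quantity, says which taxa count as anaerobes, pools them, or measures total bacterial load. If the plan is followed as written, hypothesis 7 ends with neither an estimate nor a test. If an anaerobe measure is built later, both the taxon list and the metric can be chosen after the data have been seen.

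Section 20 says that effect sizes and confidence intervals from this pilot will inform a definitive trial, and for this hypothesis there would be none. Participants also pay for the microbiome work: four stool collections, and a ten-day food diary and meal photographs that the protocol itself calls burdensome and justifies by the microbiome assessment.

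**Working it through.** **1. Does any planned measure estimate a group-level change in anaerobes?**

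| Planned measure | What it shows | Estimates the anaerobe group? |
|---|---|---|
| Observed, Chao1, Shannon | Richness or evenness, blind to oxygen tolerance | No |
| Principal coordinates | Overall dissimilarity, no direction for anaerobes | No |
| DESeq2 screen | Which single taxa differ at least 2-fold | No; taxa are neither classed nor summed |
| Fatty acids, alcohols, indoles | Metabolites; section 4 ties alcohol and fatty acids to some anaerobes only | Indirectly; no rule links them to hypothesis 7 |

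**2. What would the 2-fold screen show for a broad rise?** The cut is a chosen threshold, so there is no plan figure to reproduce. The protocol gives no baseline anaerobe share. All shares below are assumptions, the change is spread evenly over taxa, and sampling noise is ignored.

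Anaerobes go from 80% to 90% of reads:

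- each anaerobic taxon: 0.90 / 0.80 = 1.125-fold, below the cut;
- each other taxon: 0.10 / 0.20 = 0.5-fold, at the cut;
- anaerobe-to-other ratio: (0.90/0.10) / (0.80/0.20) = 9 / 4 = 2.25.

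**3. Range of baseline shares.** Suppose every anaerobe doubles in absolute amount and the other taxa do not change. With baseline share p, the new share is 2p/(1 + p), the anaerobe fold is 2/(1 + p) and the other-taxon fold is 1/(1 + p), all on the share scale.

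| p | New share | Anaerobic taxon | Other taxon | Change in ratio |
|---|---|---|---|---|
| 0.60 | 0.750 | 1.25 | 0.625 | 2.0 |
| 0.80 | 0.889 | 1.11 | 0.556 | 2.0 |
| 0.90 | 0.947 | 1.05 | 0.526 | 2.0 |
| 0.95 | 0.974 | 1.03 | 0.513 | 2.0 |

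On the share scale neither kind of taxon reaches 2-fold, although every anaerobe has doubled. DESeq2 rescales by the median taxon ratio. In an assumed table of 60 taxa, 54 of them anaerobic, that scaling gives each anaerobe a fold of 1.0 and each other taxon 0.5. The rise then appears only as a fall in the other taxa. The anaerobe-to-other ratio changes 2-fold at every baseline.

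**4. Relative versus absolute.** Start at 90%. If anaerobes double and the rest stay put, the new share is 1.80/1.90 = 0.947. If anaerobes stay put and the rest halve, it is 0.90/0.95 = 0.947. Read counts cannot separate the two, and no load measure is planned, so content in the absolute sense is not observed.

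**The case against.** The best defence is that this is one of nine hypotheses in a self-described pilot, that the primary endpoint is untouched, and that the needed data will exist. Most of that stands, and it rules out three stronger conclusions that a reader might draw.

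- **That hypothesis 7 cannot be answered.** It can, for relative abundance. Every sample is classified against SILVA, so an anaerobe share can be computed, and the faecal fermentation products are an indirect marker. What is missing is the specification.
- **That a majority group can never satisfy the 2-fold rule.** A pooled share s can rise at most 1/s-fold (1.25 at 80%, 1.67 at 60%), so above 50% it cannot double. But the rule applies to single taxa. A taxon at 5% could rise up to 20-fold, and one anaerobic taxon that triples in the 60-taxon table shows 3.0-fold and passes the cut. Nor is 1/s a strict bound under DESeq2 scaling: in a pooled two-row table a share moving from 0.80 to about 0.94 reaches 2-fold. Section 4 suggests that anaerobes are already prominent but states no majority.
- **That a real, broad shift would be reported as no significant taxa.** The cut works in both directions. In the 80% to 90% example the other taxa halve and could be flagged if their adjusted p-values were small enough. The screen would show the shift indirectly, and no rule says that such a fall counts as evidence for hypothesis 7.

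The gap remains: no definition of the quantity, no taxon list, no group-level comparison.

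**Conclusion.** The point holds as a pre-specification gap. The protocol states a directional anaerobe hypothesis and plans no measure or test of it. The per-taxon screen answers a different question and can leave every anaerobic taxon unflagged when the group has risen: about 1.13-fold per taxon for an assumed move from 80% to 90%, and 1.03- to 1.25-fold on the share scale for a true doubling from assumed baselines of 95% down to 60%. These figures assume an even, noise-free change. They illustrate the mismatch and do not predict the result. The fold of 1.0 under DESeq2 scaling further assumes that most taxa in the table are anaerobic.

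That no measure exists depends on none of these assumptions. It follows from reading sections 6, 7.2, 10.4, 14.2 and 14.4 together. The matter is secondary, but the correction is cheap and should be made.

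**What to change.** In section 10.4 (Gut microbiota), add one endpoint per stool sample: the log of the summed abundance of taxa classed as anaerobes divided by the summed abundance of the remaining classified taxa.

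- Fix the taxon list, and name the source used for oxygen tolerance, before any sequence data are analysed by condition. Timing it to unblinding would not work, because only participants are blinded and the researcher sets the oxygen fraction.
- Compare post-exposure hypoxia with post-exposure sham within person (visits 3 and 5, in whichever order they fall), with the pre-exposure samples from visits 2 and 4 as baseline.
- Report the estimate and its confidence interval, with no fold-change cut.
- Keep the diversity, ordination, DESeq2 and metabolite analyses as exploratory.
- Reword hypothesis 7 to the relative abundance of anaerobes. If absolute content is really meant, a total bacterial load measure has to be added.

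The cost is a little analysis of sequence data already planned and a short protocol edit. The drawback is that taxa which cannot be classed by oxygen tolerance at 16S resolution must be set aside; the share of reads lost this way should be reported.

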## 7. STUDY DESIGN

### 7.1 Summary of Study Design

Single blind, randomized, balanced, crossover design study (i.e. participants will undergo both the hypoxia and sham conditions and will be blinded to the conditions in which they are in).

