Visits 2-5 are identical in nature. Visits 2 and 4 are baseline visits before each arm of the crossover (i.e. the intervention). Visits 3 and 5 are following the 10 day hypoxic or sham exposures to assess the outcomes. An OGTT, body composition and venous blood samples and a stool collection will occur on each visit. After visit 3 there will be a 4 week washout out period. Visit 4 is necessary to ensure participants are back to baseline. During this visit, if anyone has had a respiratory tract infection or infectious disease in between visits, the hypoxic screening and lung function tests will be repeated. During visit 3, a new CGM sensor will be secured and accelerometer worn and a home visit for set-up will be re-booked. At the end of visit 5, another CGM and accelerometer will be affixed to the participants to check how long the effects of the intervention take to decay.

Urine collection is critical for our metabolomics analysis. In order to look for trends across time and between conditions we will need to collect urine before, during and after the intervention. Participants will be asked to collect a small urine sample for 2 days before the intervention starts, for each day of the intervention and for 2 days following the intervention. Participants will be provided with instructions on how to collect a mid-flow urine sample and how to safely store the samples until they are collected.

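### Overall gut microbiome composition is to be compared by principal coordinates analysis alone, with no test, no effect estimate and no use of the crossover pairing

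*Combined protocol and SAP*

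**What the plan says.** Section 7.2 lists the gut microbiome among the secondary outcomes, and item 7 of the hypotheses in section 6 is "Increase gut anaerobe content". Section 7.1 sets a crossover in which "participants will undergo both the hypoxia and sham conditions". Section 10, describing visits 2 to 5, says that "a stool collection will occur on each visit", which gives four stools per completer: one baseline and one post-exposure stool in each period.

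The analysis is in the Gut microbiota part of section 10.4 and has three parts:

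- Alpha diversity, by "observed diversity, Chao1 diversity and Shannon diversity metrics", with no test named.
- Overall composition: "Variability between the cohorts will be identified based on principal coordinates analysis". No distance measure, test, effect size or significance level follows.
- Individual taxa, by "generalised linear models using the DESeq2 package in R", flagged on a "2-fold difference between the cohorts with a p value (adjusted for multiple testing using Benjamini and Hochberg correction) <0.05". No participant or period term is stated.

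Section 14.2 lists the outcomes that will receive paired tests, and the microbiome is not among them. Section 14.4 says that nothing beyond the protocol's own analysis text is needed, so no other document fills the gap.

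**The concern.** Principal coordinates analysis projects a distance matrix onto a few axes. It describes how samples are spread and does not compare hypoxia with sham. The plan nevertheless uses it to identify differences, so a conclusion is expected from it. Followed as written, that conclusion rests on whether two clouds of points look apart.

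The text also speaks of cohorts, although the same people supply both sets of samples. The leading axes follow the largest source of variation. If that source is the person, a consistent shift within people can be real and hardly show on those axes. Equally, a chance separation could be reported as an effect, because no error rate is attached to the judgement. Section 20 says that effect sizes and confidence intervals from this pilot will shape a definitive trial, and for composition the plan would supply no estimate.

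**Working it through.** The documents give no power, alpha or effect size for composition, so there is no figure to reproduce. The check has three parts.

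**1. What is specified for each microbiome question**

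| Question | Method in 10.4 | Test? | Pairing used? |
|---|---|---|---|
| Alpha diversity | three metrics | none named | not stated |
| Overall composition | principal coordinates analysis | none | no |
| Single taxa | DESeq2, 2-fold and adjusted p < 0.05 | yes | not stated |

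Only the single-taxon question has a decision rule.

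**2. How much of the ordination reflects the person**

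Let ICC be the share of variation lying between people. The documents do not give it; assume 0.30 to 0.85. With four stools per person and no shift, the person share of total variation is about ICC + (1 − ICC)/4.

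- ICC 0.30: 0.30 + 0.70/4 = 0.475, about 48%.
- ICC 0.85: 0.85 + 0.15/4 = 0.8875, about 89%.
- The share passes one half when 0.75 × ICC + 0.25 > 0.5, that is, ICC above 1/3.

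**3. What a paired test would find that the axes do not show**

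Inputs:

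- Completers: 23 × 0.85 = 19.55, taken as 19 (recruitment target and 15% drop-out from the synopsis).
- Assumed: one post-sham and one post-hypoxia stool each; 100 independent Gaussian taxa; 10 taxa shifted by the stated multiple of the within-person SD; Euclidean distance; between-person SD 1 or 2 times the within-person SD (ICC 1/(1+1) = 0.5 or 4/(4+1) = 0.8).
- 300 runs per setting; 199 permutations, each swapping the two condition labels within a person at random; test at 5%.
- Axis separation: absolute difference of the condition means divided by the SD of the axis scores, on the better of axes 1 and 2.

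| Between-person SD | Shift (within-person SD) | Detected, within-person permutation | Axis separation (SD) |
|---|---|---|---|
| 1 | 0 | 0.06 | 0.13 |
| 1 | 0.5 | 0.40 | 0.16 |
| 1 | 0.75 | 0.90 | 0.19 |
| 2 | 0 | 0.07 | 0.06 |
| 2 | 0.5 | 0.44 | 0.07 |
| 2 | 0.75 | 0.94 | 0.08 |

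Independent re-runs gave 0.88 to 0.93 at 0.75 and 0.40 to 0.42 at 0.5, so the figures are stable to within simulation error. Permuting labels freely across all samples, which ignores the pairing, gave 0 detection.

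The reason is simple arithmetic. The squared length of the shift is 10 × 0.75² = 5.625, and the condition label contributes a quarter of that, 1.41, to the total variance. Total variance is 100 × (1 + 1) = 200 or 100 × (4 + 1) = 500. The true condition share is therefore 0.7% or 0.3%. That is too small to steer a leading axis, yet it is consistent within people.

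A second simulation used 50 dimensions, 13 or 20 completers, ICC 0.30 to 0.85, and total shifts of 2 or 3 units against a per-dimension SD of about 1. Power with within-person permutation was 0.59 to 1.00 (13 completers) and 0.90 to 1.00 (20 completers). With free permutation it was 0.00 to 0.73 and 0.00 to 0.99. With no shift, the within-person test rejected in 3% to 7% of runs.

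**The case against.** **DESeq2 already provides a formal test, and the hypothesis concerns anaerobes.** A reader might infer that a real hypoxia shift would go undetected. The documents do not support that, because the sentence after the ordination sets out a multiplicity-adjusted taxon-level test, and a large shift could also show on the axes. Hypothesis 7 is directional and closer to the taxon level; a global composition test has no direction and would not answer it. All of this stands.

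It does not close the gap, because DESeq2 asks a different question. In the set-up above at 0.75 SD, a paired t-test for each taxon with Benjamini-Hochberg correction and no fold threshold flagged any taxon in 51% to 59% of runs, against about 90% for the composition test. At 1.0 SD it flagged one in 92% to 93%. Without pairing it flagged one in 0% to 7% of runs at 0.75 SD. This is a stand-in; DESeq2 itself was not simulated.

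**The ordination may be meant as description.** The taxon step is the one tied to significance, so this reading is possible. The plan's verb still promises a finding, and no other method for composition is given.

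**The illustration favours the paired test.** It sets an unpaired separation on two axes against a paired test. Higher axes, and a figure with each person's samples joined, were not examined. Independent Gaussian taxa are not 16S counts. This stands: the figures show a mechanism and are not estimates for this trial. The test also misses most shifts of 0.5 SD.

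**Read depth.** A reader might also infer an error from the absence of an equal-depth step for the richness metrics. Common-depth subsampling is one normalisation choice among several and it discards data. Silence on it in a protocol is not a fault, and nothing above bears on it.

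**Conclusion.** The gap is real and limited. For overall composition the plan relies on an ordination that gives no test or effect estimate and does not use the pairing. A modest within-person shift could be obscured, or a chance separation could be judged by eye.

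Under the assumed inputs, a test permuted within participant detects about 90% of 0.75 SD shifts and about 40% of 0.5 SD shifts. Axis separation moves only from 0.13 to 0.19 SD, or from 0.06 to 0.08 SD, between no effect and the 0.75 SD shift. These sizes rest on 19 completers, independent taxa and a between-person share that the documents do not give. A reader might infer that the ordination must mainly show differences between people. That follows only if the between-person share exceeds about one third, which is plausible with four stools per person but not documented.

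This is a secondary outcome in a self-described pilot, and the primary glucose result is unaffected. The change is worth making because it is cheap and gives the later trial an estimate to use.

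**What to change.** Amend the Gut microbiota text of section 10.4, or add to 14.2:

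- Keep the principal coordinates analysis as a descriptive figure, and name the distance measure.
- Test post-hypoxia against post-sham stools on that distance with PERMANOVA or an equivalent, permuting condition labels only within participant. With 19 completers there are 2^19 = 524,288 arrangements, so small p values are attainable.
- Account for period. An odd number of completers such as 19 cannot split equally between the two sequences, so a period effect would not cancel exactly.
- Where feasible, use the baseline stools from visits 2 and 4, for example by comparing changes from each period's baseline as a supporting analysis.
- Report R-squared and p, with a check that dispersion is similar in the two conditions.
- In the same amendment, say whether the DESeq2 model carries a participant term.

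The cost is a few sentences and a few lines of R, which section 10.4 already uses. No new samples or visits are needed. The downside is a little more analysis to run and report.

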### 14.2 Analysis of Endpoints

All data will be tested for normality using the Shapiro-Wilk test. For normally distributed data, paired samples t-tests will be used to assess differences pre and post hypoxic exposures for; blood [glucose] (AUC and peak), insulin sensitivity, eHSP70, IL-6, leptin, ghrelin, TNFa, SOD, HIF-1 $\alpha$  HR, PA and sleep efficiency. For non-parametric data Wilcoxon-Signed rank test will be used for pairwise comparisons. Repeated measures one-way analysis of variance (ANOVA) will be used to identify differences between conditions for SpO2 and [glucose] across time from the CGMs. Mauchly's test of sphericity will be used to determine if any data violated the assumption of spherical data. If violated, sphericity will be accounted for using the Greenhouse-Geisser correction. Where significant differences are observed ( $P < 0.05$ ), post-hoc tests will be performed using LSD pairwise comparisons. Effect sizes will be reported as partial eta squared ( $\eta^2_p$ ) (small = 0.01; medium = 0.06; large = 0.14) [33].

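### The microbiome taxa test is worded as a comparison of undefined 'cohorts' with no participant term, although each person gives four stool samples; run as worded, it would lose power

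*Combined protocol and SAP*

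**What the plan says.** Section 7.1 describes a crossover in which "participants will undergo both the hypoxia and sham conditions". In Section 10, under Intervention, "Visits 2 and 4 are baseline visits before each arm of the crossover", visits 3 and 5 follow the exposures, and "An OGTT, body composition and venous blood samples and a stool collection will occur on each visit". A completer therefore gives four stool samples: before and after hypoxia, and before and after sham.

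Section 10.4 (Gut microbiota) sets out the analysis:
- Ordination: "Variability between the cohorts will be identified based on principal coordinates analysis".
- Taxa: "Significantly differentially abundant taxa will be identified between each cohorts' sample", "based on the use of generalised linear models using the DESeq2 package in R".
- Rule for calling a taxon different: a "2-fold difference between the cohorts with a p value (adjusted for multiple testing using Benjamini and Hochberg correction) <0.05".

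It also lists three alpha-diversity measures without naming a test for them. No design formula, participant term, period term or contrast is given.

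Section 14.2 says "paired samples t-tests will be used to assess differences pre and post hypoxic exposures for" a list of outcomes that does not include the microbiome, and adds a general signed-rank rule for non-parametric data. Section 14.4 states that nothing further is required by way of a SAP.

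**The concern.** A crossover with one randomised group has no cohorts to compare. The natural comparisons are between samples from the same people: pre against post, post-hypoxia against post-sham, or change against change. Section 10.4 names none of these, and its wording is that of a comparison between separate groups. An analyst who followed it literally would give DESeq2 a group label and no participant factor. Stable differences between people would then stay in the error term, although the crossover makes it possible to remove them.

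Gut microbiome is a listed secondary outcome, and hypothesis 7 (more gut anaerobes) depends on it. Section 10.4 (Diet diary) asks participants to record and photograph meals for all 10 days so that diet can be replicated in both conditions. It ties this to the microbiome and acknowledges the burden. That effort serves a within-person comparison, which the stated analysis does not specify.

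**Working it through.** The plan gives no sample size, power or error rate for the microbiome, so there is no figure to reproduce.

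**Inputs**
- Participants: 23 planned (Section 8.2) with 15% drop-out (Section 2), so 23 × 0.85 = 19.55, taken as n = 20 completers. Section 14.1 analyses completers only.
- Samples: four per completer (Section 10, visits 2 to 5).
- Within-person correlation r of a taxon's abundance: not given. Assumed, over the range 0 to 0.9.
- Outcome model: normal with equal variance σ², as a surrogate for the DESeq2 count model. Results are per taxon at a nominal two-sided 0.05, before Benjamini-Hochberg.

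**Standard error for one contrast, post-hypoxia against post-sham**
- Unpaired: σ√(2/n).
- Paired: σ√(2(1 − r)/n).
- Ratio: 1/√(1 − r).

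This gives 1/√0.5 = 1.41 at r = 0.5, 1/√0.3 = 1.83 at r = 0.7, 1/√0.2 = 2.24 at r = 0.8, and 1 at r = 0.

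**Error rate and power by simulation (10,000 runs, n = 20, true difference 0.5 SD for power)**

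| r | SE ratio | Type I error, unpaired | Power, unpaired | Power, paired |
|---|---|---|---|---|
| 0 | 1.00 | 5.1% | 34% | 32% |
| 0.3 | 1.20 | 1.9% | 31% | 43% |
| 0.5 | 1.41 | 0.7% | 28% | 56% |
| 0.7 | 1.83 | 0.05% | 24% | 78% |
| 0.9 | 3.16 | about 0% | 17% | above 99% |

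Using all four samples as if independent, with two per person on each side of a within-person contrast, gives the same direction. Type I error is 2.0%, 0.7%, 0.04% and about 0% at r = 0.3, 0.5, 0.7 and 0.9.

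**Dependence on the contrast**

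The ratio 1/√(1 − r) holds only when the contrast is unchanged. Under equal correlation among the four samples, the paired standard error of the condition-by-visit contrast (difference in pre-to-post change) is 2σ√((1 − r)/n). That is √2 = 1.41 times the paired post-against-post standard error. Set against an unpaired post-against-post test, the gain factor falls to 1/√(2(1 − r)): 1.00, 1.29 and 1.58 at r = 0.5, 0.7 and 0.8. At r = 0.5, changing to that contrast uses up the whole gain from pairing.

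**The case against.** The strongest reply is that the plan is silent rather than wrong. It never says the samples are independent, a DESeq2 model can carry a participant factor, and 'cohorts' may be loose wording for the two conditions. This stands as far as it goes: the documents do not show that pairing will be dropped. But Section 10.4 is the whole plan for this outcome, and its literal reading is the inefficient one.

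A reader might infer several stronger things that the documents do not support:
- *That unreliable positive taxa would be reported.* For within-person contrasts the error runs the other way, with type I error below 5%. Inflation (16% at r = 0.3 to 33% at r = 0.9) appeared only for a between-person contrast: two sequence groups of 10, with each person's four samples treated as independent. The plan names no such contrast.
- *That the ordination has a wrong error term.* Section 10.4 states no hypothesis test for the principal coordinates analysis.
- *That alpha diversity has no paired test.* The signed-rank rule in Section 14.2 is worded generally and may be meant to cover it. It cannot cover DESeq2.
- *That the microbiome was singled out.* The list in Section 14.2 also leaves out body composition, nitrite, food intake and metabolomics.
- *That a condition-by-visit test is required.* The primary endpoint is a post-intervention comparison, and a matching contrast for taxa is legitimate and, under equal correlation, more precise.

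**Conclusion.** The point holds as a fault in how the differential-abundance analysis is specified. It is worded as a between-group comparison, contains no participant term and names no contrast, in a design with four samples per person. If it is run as worded, the standard error of a within-person contrast is 1.41 to 2.24 times what it need be at r = 0.5 to 0.8. At 20 completers and a 0.5 SD difference, per-taxon power is 28% instead of 56% at r = 0.5, and 24% instead of 78% at r = 0.7. The harm is missed taxa.

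These sizes rest on an assumed correlation, equal correlation across visits where four samples are used, and a normal surrogate for a count model before multiplicity adjustment, so they are indicative. At r = 0 there is nothing to gain (34% against 32%). The primary glucose analysis is unaffected.

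**What to change.** In Section 10.4 (Gut microbiota):
1. Replace 'cohorts' with a named within-person contrast. Post-hypoxia against post-sham would match the primary endpoint. The condition-by-visit contrast is an alternative, but it is less precise if correlation is equal across visits.
2. State the DESeq2 design, with participant as a blocking factor plus period and condition, and keep the fold-change threshold and Benjamini-Hochberg rule as they are.
3. Confirm that the paired tests of Section 14.2 apply to the alpha-diversity measures, and for which contrast.
4. If a permutation test is added to the ordination, restrict permutations to within participant.

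The cost is a few lines of text and a design formula. No extra samples, visits or sequencing are needed.
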